# **Brief summary**

The purpose of the study is to assess whether lung ultrasound is able to detect lung injury after lung resection surgery.

# **Detailed description**

Postoperative pulmonary complications (PPC) are common after lung resection surgery, with an incidence that ranges between 11-32%. As PPC are associated with worse outcomes, many studies aim to find predictors that identify high risk patients and prompt specific interventions and/or monitoring and hence, improve outcomes. PPC result from lung injury inherent to lung resection surgery. Lung aeration changes seen with lung ultrasound (LUS) could detect lung injury and thus, identify patients at high risk of PPC. The underlying mechanisms of lung injury are different in the dependent and non-dependent lung; oxidative stress in both lungs, lung injury associated with one-lung ventilation in the dependent lung and ischemia/reperfusion or surgical manipulation in the non-dependent lung. LUS evaluates the dependent and non-dependent lung separately and so it can be valuable in understanding the characteristics and intensity of lung injury in each lung specifically.

This is a prospective, single-centre, observational study in which 30 consecutive participants with non-small cell lung cancer scheduled for lung resection via VATS will be recruited. Participants will be divided in two groups depending on the size of the resection. First group will be resection less than lobectomy. Second group will be resection equal to or greater than lobectomy. Participants will be recruited consecutively until there are 15 patients in each group. LUS will be performed in each participant's operated and non-operated lung at three predefined time points: before surgery, after extubation and 24 h after surgery. Each hemithorax will be divided into 6 areas: anterior, lateral and posterior, separated by the anterior and posterior axillary lines, each divided into upper and lower zones. For each echographic examination, cineloops of the most pathological findings in each area will be stored and analysed offline by two independent and blinded anaesthesiologists. From these, a semiquantitative score, the modified lung ultrasound score (mLUSS), will be calculated for each hemithorax to assess lung aeration at each time point. The level of agreement for mLUSS will be tested. At the same predefined time points blood plasma samples will be collected, flash-frozen and stored in order to measure levels of the inflammatory mediators IL-6, IL-10 and TNF $\alpha$ .

The investigators hypothesise that LUS can detect lung injury after lung resection surgery. The primary objective of the study is to assess changes in lung aeration after lung resection with mLUSS. Secondary objectives are, first, to describe LUS findings after lung resection surgery, second, to assess the ability of mLUSS to detect oxygenation changes after lung resection and third, to compare the behaviour of inflammatory mediators in plasma with mLUSS changes.

## **Outcome measures**

## 1. Primary outcome measure

Title: change in mLUSS after lung resection. Description: the modified lung ultrasound score (mLUSS) ranges 0-36; the higher the score, the less aeration (worse). Timeframe: preoperative vs immediate postoperative period vs 24 hours after surgery.

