## 2. Secondary outcome measures

- Title: LUS findings in the dependent and non-dependent lung. Description: description of LUS findings after lung resection surgery in each lung. Timeframe: preoperative vs immediate postoperative period vs 24 hours after surgery.

- Title: changes in oxygenation (PAFI) after lung resection. Description: PAFI is the ratio between paO2 and fraction of inspired oxygen; the lower, the worse. Timeframe: preoperative vs immediate postoperative period vs 24 hours after surgery.

- Title: changes in plasma cytokine IL-6 after lung resection. Timeframe: preoperative vs immediate postoperative vs 24 hours after surgery.

- Title: changes in plasma cytokine IL-10 after lung resection. Timeframe: preoperative vs immediate postoperative vs 24 hours after surgery.

- Title: changes in plasma TNF $\alpha$  after lung resection. Timeframe: preoperative vs immediate postoperative vs 24 hours after surgery.

- Title: changes in blood bone natriuretic peptide (BNP) after lung resection. Timeframe: preoperative vs immediate postoperative vs 24 hours after surgery.

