#### **Detailed examinations**

#### -Ultrasound

Lung ultrasound (LUS) will be performed in each participant's dependent and non-dependent lung. Participants will be placed in a semi-recumbent position. Each hemithorax will be divided into 6 areas: anterior, lateral and posterior, separated by the anterior and posterior axillary lines, each divided into upper and lower zones. First, for each zone, subcutaneous emphysema (no emphysema, mild or moderate) and the feasibility of ultrasound evaluation (feasible, non-feasible) will be deemed. The focus will be set just below the pleural line. For each echographic examination, the most pathological area will be evaluated. The pleural line will be assessed for mobility (no mobility, lung pulse or lung sliding) and shape (regular or irregular). Specifically, the pleural line will be checked on the 2nd and 3rd intercostal space to assess the presence and extent of pneumothorax. B-lines will be counted (0-10) and lung consolidations (none, subpleural, translobar) will be looked for. A semiquantitative score, the modified lung ultrasound score (mLUSS), will be calculated for each hemithorax to assess lung aeration at each time point. The presence and size of pleural effusion will also be assessed in the most dependent region for each hemithorax. Cineloops will be stored and analysed offline by another independent and blinded anaesthesiologist. The level of agreement for mLUSS will be tested.

Diaphragm thickening fraction will be assessed at the zone of apposition located in the midaxillary line between the eight and tenth ribs in a semi-recumbent position. Thickness will be measured from the inside edge of the diaphragmatic pleura to the inside edge of the peritoneal membrane at the end-expiration (EE) and end-inspiration (EI). The percent change in diaphragmatic thickness will be calculated by ([thickness at EI - Thickness at EE]/Thickness at EE).

Hand-held echocardiography will be performed. Feasibility will be deemed (feasible, non-feasible). Ejection fraction of the left ventricle will be visually assessed (normal function, mild or moderate dysfunction). Left heart preload and diastolic function will be evaluated with the following parameters: E wave, A wave, E/A, e' wave, E/e' and lateral S' wave. Right heart systolic function will be evaluated with lateral S' wave.

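### Does the primary outcome's 0-36 range leave open whether mLUSS is a two-lung total or a per-lung score?

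*Protocol*

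**What the plan says.** The protocol's primary outcome measure is headed "Title: change in mLUSS after lung resection" and described as follows: "the modified lung ultrasound score (mLUSS) ranges 0-36; the higher the score, the less aeration (worse". It is assessed before surgery, immediately after surgery and at 24 hours. The primary objective in the Detailed description is equally general: "The primary objective of the study is to assess changes in lung aeration after lung resection with mLUSS".

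The ultrasound methods split each hemithorax into 6 areas and then state: "A semiquantitative score, the modified lung ultrasound score (mLUSS), will be calculated for each hemithorax to assess lung aeration at each time point". The Detailed description says the same, and gives the reason for looking at the lungs one by one: "LUS evaluates the dependent and non-dependent lung separately", with different mechanisms of injury expected in each.

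Among the secondary outcomes is a per-lung item: "description of LUS findings after lung resection surgery in each lung".

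The two accounts of the examination also differ in one phrase. The ultrasound methods say "For each echographic examination, the most pathological area will be evaluated", whereas the Detailed description says "cineloops of the most pathological findings in each area will be stored".

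No section gives the points awarded per area, and none says that the two hemithorax scores are added.

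**The concern.** The only mLUSS whose construction is described is a hemithorax score, yet the primary outcome has one range and names no lung. Taken alone, that could leave the two-lung total, the operated lung or the non-operated lung as the primary variable.

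The unit affects interpretation: a 3-point change is 3/36 = 8% of a 0-36 scale and 3/18 = 17% of a 0-18 scale. It also affects sensitivity, because a total dilutes a change confined to one lung and gains when both lungs change. If the unit were still open when results were seen, the most favourable of the three could be presented as primary.

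The phrase in the ultrasound methods about the most pathological area adds to the doubt. Read literally, it describes evaluating one area per examination, which would not yield a 6-area score.

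**Working it through.** **Inputs.** Areas per hemithorax: 3 regions × 2 zones = 6, so 12 over both lungs (Detailed examinations, Ultrasound). Stated range: 0-36 (Primary outcome measure). Points per area: not stated, so varied here as an assumption.

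**Formula.** Maximum score = number of areas × maximum points per area.

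| Maximum points per area (assumed) | Hemithorax maximum (6 areas) | Two-lung maximum (12 areas) |
|---|---|---|
| 2 | 12 | 24 |
| 3 | 18 | 36 |
| 4 | 24 | 48 |
| 5 | 30 | 60 |
| 6 | 36 | 72 |

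**Reproducing the plan's figure.** The value 36 arises in two ways: 36/12 = 3 points per area for the two-lung sum, or 36/6 = 6 points per area for one hemithorax. Under any single scoring rule, the total and a per-lung score cannot both run from 0 to 36. The range therefore narrows the choice. At 0-3 per area, a per-lung primary variable would run 0-18 and contradict the stated range. A per-lung primary variable needs 0-6 per area, for which the protocol offers no support.

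**The other sections.** Calculating a score for each hemithorax describes how it is obtained and is compatible with adding the two scores. The primary objective speaks of aeration after resection without singling out a lung. Per-lung findings appear as a descriptive secondary outcome. All three fit a total as primary.

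**The area wording.** The ultrasound methods define 6 areas and make their first assessments zone by zone, and the Detailed description has loops stored for every area. Read together, each area is scored on its worst finding. The singular phrase is loose drafting and does not bear on the choice between total and per-lung score.

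**The case for a change.** The strongest case for a change is that the identity and scale of a primary variable belong in the protocol, not in an analysis plan. The inference to a total rests on a scoring rule the protocol never writes down. The protocol's own rationale, with different injury in each lung, points towards per-lung scores, and the per-lung secondary outcome concerns ultrasound findings in general, so it does not expressly make the hemithorax mLUSS secondary.

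Figures can be attached to this. Take 28 participants, one before-after contrast, a two-sided 5% paired t-test, equal SDs and a between-lung correlation of 0 to 0.5. If nothing changes, the chance that at least one of total, operated lung and non-operated lung is significant is about 10% to 12%, against 5% for one named variable. With a per-lung change of 0.55 SD (80% power for one lung), the total has 37% to 51% power if one lung changes and 90% to 98% if both change equally.

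What stands is that the summation and the points per area are not written down, so the reading as a total is strong but inferred. The figures add little. The protocol states that no sample size was calculated, and it sets no significance level, power or primary test. The 0.55 SD effect was chosen to give 80% power and comes from nowhere in the document. One paired contrast also ignores the three time points and the two resection groups. The error rate presumes that all three variables are tested and the best is reported, although the stated range counts against two of them. The power comparison runs both ways, so it shows no harm from using the total.

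**Conclusion.** The concern does not call for a change. The 0-36 range is not shown to be wrong, and no two sections contradict each other arithmetically. Assuming 0-3 points per area, the range is exactly that of the sum over 12 areas, with 0-18 for each hemithorax. The competing reading needs 0-6 per area and a 0-72 total, which nothing in the protocol suggests.

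What remains is an unwritten scoring detail that an analyst would complete from the stated range and the list of secondary outcomes. The area scores of both lungs are recorded at every time point, so either summary can be computed and nothing is lost in data collection. Neither unit is better in all cases, and the study is a single-centre observational one with no power calculation that depends on the choice. The difference in area wording is a clerical slip that the surrounding text resolves.

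This conclusion rests on the 0-3 assumption and on reading the hemithorax calculation as a step towards the total. If the sponsor's scoring were in fact 0-6 per area, 0-36 would be a per-lung range and the reading would have to be revisited.

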## 2. Secondary outcome measures

- Title: LUS findings in the dependent and non-dependent lung. Description: description of LUS findings after lung resection surgery in each lung. Timeframe: preoperative vs immediate postoperative period vs 24 hours after surgery.

- Title: changes in oxygenation (PAFI) after lung resection. Description: PAFI is the ratio between paO2 and fraction of inspired oxygen; the lower, the worse. Timeframe: preoperative vs immediate postoperative period vs 24 hours after surgery.

- Title: changes in plasma cytokine IL-6 after lung resection. Timeframe: preoperative vs immediate postoperative vs 24 hours after surgery.

- Title: changes in plasma cytokine IL-10 after lung resection. Timeframe: preoperative vs immediate postoperative vs 24 hours after surgery.

- Title: changes in plasma TNF $\alpha$  after lung resection. Timeframe: preoperative vs immediate postoperative vs 24 hours after surgery.

- Title: changes in blood bone natriuretic peptide (BNP) after lung resection. Timeframe: preoperative vs immediate postoperative vs 24 hours after surgery.

# Methods

This study was first approved by the Clinical Investigation Ethics Committee of the General University Hospital of Valencia on 25th October 2018, with a later amendment approved on 6th November 2020, before the beginning of recruitment.

## 1. Study groups

This is a prospective, single-centre, observational study in which 30 consecutive participants with non-small cell lung cancer scheduled for lung resection via VATS will be recruited. Participants will be divided in two groups depending on the size of the resection. First group will be resection less than lobectomy. Second group will be resection equal to or greater than lobectomy. Participants will be recruited consecutively until there are 15 patients in each group. Sample size has not been calculated, as there is no previous information on changes in lung aeration after lung resection. Sample size will be set in 28 participants, adding 5% (30 participants in total) to compensate for possible losses.

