#### 2. Elegibility

Inclusion Criteria:
Age > 18
ASA I-III
Non-small cell lung neoplasm
Elective lung resection
Via VATS
Under one-lung ventilation

**Exclusion Criteria:** -Pregnancy Respiratory tract infection the previous month Diagnosed pulmonary fibrosis Predicted FEV < 40% Surgery limited to biopsy Surgery that includes resection of the thoracic wall or the diaphragm Neoplasm metastasis Obesity class II or more (BMI  $\ge$  35 kg/m^2) Risk of malnutrition CONUT > 1 Hemoglobin < 10 g/dlChronic kidney failure: glomerular filtration < 60 ml/min/m^2, nephrectomy, kidney transplantation Treatment with corticosteroids or immunosuppressive agents 3 months before surgery Transfusion of blood products during the previous 10 days Heart failure (New York Heart Association Functional Class 3 or 4) during the week before surgery. Heart valve diseases over stage B of the American College of Cardiology/American Heart Association Task Force on Practice Guidelines 2014 **Diastolic dysfunction** 

Recruited participants will be excluded in the following cases:

Intraoperative or postoperative blood product transfusion (first 24 h) Pleurodesis Need to convert to thoracotomy

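### The larger-resection group has no upper limit, so it admits pneumonectomy, after which the operated-side mLUSS and the 0-36 total do not measure aeration

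*Protocol*

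**What the plan says.** - **Group definition.** The Protocol (Detailed description and 1. Study groups) splits participants by size of resection. The smaller group is anything short of lobectomy. For the larger one: "Second group will be resection equal to or greater than lobectomy". No upper limit is set. Recruitment is consecutive until each group holds 15.
- **Exclusions.** Under 2. Elegibility, the exclusions by type of surgery are biopsy only and "Surgery that includes resection of the thoracic wall or the diaphragm". Participants already recruited are removed for transfusion in the first 24 hours and for "Pleurodesis Need to convert to thoracotomy". Pneumonectomy appears in neither list, nor anywhere else in the Protocol.
- **Primary outcome.** It is the change in mLUSS, a score from 0 to 36 on which higher values mean less aeration, compared between the preoperative, immediate postoperative and 24-hour assessments.
- **Measurement.** "LUS will be performed in each participant's operated and non-operated lung at three predefined time points" (Detailed description). The score "will be calculated for each hemithorax to assess lung aeration at each time point" (Ultrasound). On the areas: "Each hemithorax will be divided into 6 areas: anterior, lateral and posterior, separated by the anterior and posterior axillary lines", each split into an upper and a lower zone.
- **Zones that cannot be assessed.** For each zone, "the feasibility of ultrasound evaluation (feasible, non-feasible) will be deemed". The Protocol does not say how a non-feasible zone, or a side without lung, enters the score.

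**The concern.** The group definition and the measurement plan do not fit together at the upper end of resection. After a pneumonectomy the operated hemithorax contains air or fluid and no lung. The six areas on that side can still be scanned and given a number at both postoperative points, but that number says nothing about aeration. The change from baseline on that side would reflect removal of the organ, whereas the study hypothesis concerns injury to lung that remains.

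The same number would pass into the secondary description of findings in the non-dependent lung, and into the objectives that set mLUSS against oxygenation and inflammatory mediators. Because recruitment is consecutive, the Protocol gives no ground for passing over a participant who meets its criteria and is scheduled for a thoracoscopic pneumonectomy.

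**Working it through.** **Inputs from the Protocol**
- mLUSS range 0-36 (1. Primary outcome measure).
- 6 areas per hemithorax, both sides scanned (Detailed description; Ultrasound).
- 15 participants per group; 28 participants plus 5% gives 30 (1. Study groups).
- No standard deviation, no effect size and no expected number of pneumonectomies are given.

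**Step 1: the plan's own figures**
- Sample size: 28 × 1.05 = 29.4, and 28 / 0.95 = 29.47. Both round up to 30, as stated.
- Scale: 2 sides × 6 areas = 12 areas, and 36 / 12 = 3 points per area. The 0-36 range therefore fits a sum over both sides. The 3 points per area are inferred; the Protocol does not state them.

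**Step 2: share of the score with no lung beneath it**
- Operated side: 6 × 3 = 18 points, and 18 / 36 = 50% of the total.
- Non-operated side: the other 18 points, still a measure of aeration.

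**Step 3: how far the arbitrary part can move one participant**
- Let s be the preoperative operated-side score and x the number given to that side after surgery, each between 0 and 18. The recorded change is x − s.
- All six areas read as 0: the change is −s.
- All six areas read as 3: the change is 18 − s.
- The gap between the two readings is (18 − s) − (−s) = 18 points, whatever s is.

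**Step 4: ceiling on the mean change**

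With k such participants, the ceiling is 18k/15 in the larger-resection group and 18k/30 overall. The values of k are assumed.

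| k | Larger-resection group (n = 15) | All participants (n = 30) |
|---|---|---|
| 0 | 0 | 0 |
| 1 | 1.2 | 0.6 |
| 2 | 2.4 | 1.2 |
| 3 | 3.6 | 1.8 |

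If losses bring the numbers down to 14 and 28, one such participant gives at most 18/14 = 1.29 and 18/28 = 0.64.

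On the 36-point scale, 1.2 is 3.3% and 0.6 is 1.7%.

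**The case against.** **Pneumonectomy is never named.** A resection larger than a lobectomy may be a bilobectomy, or a lobectomy with a further resection. Several procedures also presuppose lung on the operated side: a measurement after recruitment in two-lung ventilation listed after the one-lung stage, air-leak recording for all, and a described mechanism of injury in the non-dependent lung. The authors may have had an unstated boundary in mind. This stands as a reading of intent, and it means nobody should infer that the study plans to enrol pneumonectomies. It does not change what the criteria admit, and it shows that the definition and the procedures disagree.

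**It may never happen.** The operation must be thoracoscopic, and conversion to thoracotomy removes the participant. This stands: no frequency is given, and the number may be zero.

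**There are partial safeguards.** Zones are flagged for feasibility, and the score is formed per hemithorax, so the non-operated side can be separated. The second part stands in full, and a reader who inferred that all of such a participant's ultrasound data are worthless would go too far. The feasibility flag helps less. It carries no scoring rule, and a space filled with air or fluid can be imaged, judged feasible and scored by blinded readers working from stored loops.

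**The scoring of missing zones belongs in a SAP.** That is fair for the scoring rule, and its absence is not the point here. Who belongs to a group and who is excluded are fixed in the Protocol, and those statements are what admit the invalid value.

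**The size is a ceiling.** This also stands. A rise of 18 points from baseline needs every operated-side area to go from 0 to 3. Against a lobectomy participant whose own operated-side score rises, the net upward shift is smaller. A claim of visible influence on the results is not supported, because no standard deviation is given.

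**Conclusion.** The point holds in a limited form. As written, the criteria admit pneumonectomy and the plan scores the operated side regardless. For such a participant 18 of the 36 points of the primary score would not measure aeration at either postoperative time point. The defect is confined to the operated-side score and the 0-36 total.

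Its size is at most 1.2 points on the mean change of the larger-resection group and 0.6 points on the overall mean, per such participant. The direction is unknown, since it depends on how the space is read. These figures rest on 3 points per area and on full groups of 15 and 30.

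The documents do not show that any such participant will be enrolled, so the actual effect may be nil. This is a cheap improvement that is worth making, because the stated rules would otherwise put an invalid value into the primary outcome.

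**What to change.** Limit the larger-resection group to resections that leave lung on the operated side: list pneumonectomy among the exclusions under 2. Elegibility, and align the group definition in the Detailed description and in 1. Study groups. A participant removed on this ground is replaced under the existing rule of recruiting to 15 per group.

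If such participants are to be kept, state that after surgery their operated side and 0-36 total are left out of the primary outcome, and that only the non-operated hemithorax is reported.

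The cost of the first option is a rare replacement and a conclusion that does not cover pneumonectomy; little is lost, since mLUSS cannot assess aeration on that side in any case. Without replacement, the exclusion would draw on the allowance of two (30 − 28), which transfusion, pleurodesis and conversion already share. The second option leaves eligibility unchanged, but the primary analysis then has fewer participants than were recruited.

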#### Anaesthesia protocol

Analgesia will be administered via a paravertebral catheter in the non-dependent hemithorax of participants undergoing a resection equal to or greater than lobectomy, with an initial dose of 0'25% levobupivacaine (0'3 ml/kg) followed by subsequent boluses of 0'25% levobupivacaine 6-10 ml every hour. Analgesia will be administered via an erector spinae single shot block in the non-dependent hemithorax of participants undergoing rection less than lobectomy, with 0'25% levobupivacaine (0'3 ml/kg) plus infiltration of the ports at the end of the procedure with levobupivacaine 0'25%. Anaesthesia will be induced with propofol (2 to 3 mg/kg) and fentanyl (2-3 mcg/kg). Neuromuscular blockade will be achieved with rocuronium (0.6 to 1 mg/kg). Orotracheal intubation will be performed with a left double-lumen tube (35 to 37 Fr in women and 39 to 41 Fr in men). Correct placement will be verified by direct visualisation with a fibreoptic bronchoscope. All patients will be managed using a Perseus ventilator (Drägerwerk). Volume-controlled ventilation will be used during two-lung ventilation (TLV) with the following parameters: tidal volume 7 ml/kg (predicted body weight); inspiratory pause 25%, positive end-expiratory pressure (PEEP) 5cmH2O; fraction of inspired oxygen (FiO2) 0.4 to 0.5; and respiratory

rate to maintain end-tidal carbon dioxide pressure (ETCO2) at 35 to 45 mmHg. Hypnosis will be maintained with sevoflurane at the necessary concentrations to maintain a bispectral index of between 40 and 60. A continuous infusion of rocuronium will be used to achieve profound neuromuscular blockade with train of four (TOF) of 0. A continuous infusion of remifentanil 0.1-0.3 mcg/kg/min will be used to achieve hemodynamic stability after having administered levobupivacaine through the paravertebral catheter, in the cases where there is a catheter. Intermittent pneumatic compression stocks and convective warming blanket will be systematically used.

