#### Postoperative course: Immediate postoperative period

Depending on factors related to surgery and to participants, postoperative care will take place in the ICU or PACU.

At their arrival at ICU or PACU, chest drains will be connected to aspiration -20 cmH2O, and for those participants in whom there is an indwelling paravertebral catheter, continuous infusion of levobupivacaine 0'125% at 10-12 ml/h will be used until 72 h after surgery.

Examinations will include the following (explained at the end of the protocol):

- ultrasound including lung, diaphragm and echocardiography.
- blood analysis for measurement of inflammatory mediators, as well as blood count and chemistry.
- chest X-ray

The following data will be registered: SpO2, FiO2, heart rate, median arterial pressure, analgesia using visual analogue scale (VAS) at rest and presence of air leak through chest drains.

All participants will receive supplemental oxygen FiO2 0.4 through a venturi mask at least during the first postoperative hour. 15-30 minutes after arrival at ICU, if the participant is fully awake with Glasgow comma scale (GCS) > 13, is not agitated with Richmond Agitation-Sedation Scale (RASS) -1 to +1, has adequate analgesia level VAS < 4 and SpO2  $\geq$ 97% with venturi mask FiO2 0.4, an Air-Test will be performed. Oxygen mask will be removed and participants will be left breathing room air for at least 5 min while continuously monitoring SpO2. The Air-Test will be considered positive when the recorded SpO2 is  $\leq$ 96% and negative when SpO2 is  $\geq$ 97%. The oxygen mask will be placed back whenever SpO2 falls to 92% for more than 1 min during the Air-Test. Once the Air-Test is completed an arterial blood gas analysis will be done while breathing room air. Incentive spirometry will then be started.

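### Do the two resection groups of 15 undermine the secondary objectives that relate mLUSS to oxygenation and cytokines?

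*Protocol*

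**What the plan says.** Section 1 (Study groups) states "Participants will be divided in two groups depending on the size of the resection", with the line drawn at lobectomy, and then "Participants will be recruited consecutively until there are 15 patients in each group". The same text stands in the Detailed description.

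The objectives do not mention the groups. The primary objective concerns the change in mLUSS after resection. Two secondary objectives link variables. One, on blood gases, reads "second, to assess the ability of mLUSS to detect oxygenation changes after lung resection". The other closes the list of objectives and turns to the cytokines: "to compare the behaviour of inflammatory mediators in plasma with mLUSS changes". The outcome measures compare three time points and also name no group.

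Two places suggest that the groups might differ. The Detailed description lists "ischemia/reperfusion or surgical manipulation in the non-dependent lung" among the mechanisms of injury. The Anaesthesia protocol ties regional technique to group: "Analgesia will be administered via a paravertebral catheter in the non-dependent hemithorax of participants undergoing a resection equal to or greater than lobectomy", against "Analgesia will be administered via an erector spinae single shot block in the non-dependent hemithorax of participants undergoing rection less than lobectomy". For patients with a catheter, a continuous infusion "will be used until 72 h after surgery", which spans both postoperative measurements.

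The Protocol has no statistical analysis section. It prescribes neither a pooled analysis nor adjustment or stratification by group.

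**The concern.** A design that fills two strata to a fixed quota and then never mentions them invites the question of what they are for. The worry is sharpest for the two association objectives. Suppose larger resections produce both a worse mLUSS and worse oxygenation or higher cytokines. A correlation over all 30 patients could then look favourable even if mLUSS says nothing about oxygenation or inflammation among patients with the same operation. If the groups differed in conflicting directions, a real patient-level link could be hidden. Because analgesic technique goes with group, a group difference could not be credited to resection size alone.

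A lesser point is that, under a quota, enrolment is consecutive only within each group, so an overall mLUSS change describes an equal mix of the two kinds of resection rather than the centre's natural case mix.

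**Working it through.** **The plan's own figure.** Section 1 gives 28 participants plus 5% for losses: 28 × 1.05 = 29.4, or 28 / 0.95 = 29.5. Both round up to 30 = 2 × 15. The 28 has no derivation, and the Protocol says that none was made.

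**Assumptions, none from the Protocol.** Changes are correlated across patients, data are normal, and the test is a two-sided 5% Pearson test. The within-group correlation is r_w, and the group means differ by d1 and d2 within-group SDs on the two variables. A positive product d1·d2 means that the group difference points the same way as the expected association.

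**Formula.** With a share p of patients in one group,

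r_pooled = [r_w + p(1−p)·d1·d2] / √{[1 + p(1−p)·d1²]·[1 + p(1−p)·d2²]}.

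**No within-group association, aligned differences, 15/15.** With r_w = 0 and d1 = d2 = d, this becomes (d²/4)/(1 + d²/4). At d = 1 it is 0.25/1.25 = 0.20. Rejection rates are from simulation.

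| d | pooled r | positive, pooled | positive, adjusted for group |
|---|---|---|---|
| 0.5 | 0.06 | 6% | 5% |
| 0.8 | 0.14 | 11–12% | 5% |
| 1.0 | 0.20 | 19% | 5% |
| 1.5 | 0.36 | 54% | 5% |

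**True within-group correlation of 0.5.**

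- Opposing differences of 1 SD: (0.5 − 0.25)/1.25 = 0.20. Power is 15% pooled against 81% adjusted.
- Opposing differences of 0.5 SD: (0.5 − 0.0625)/1.0625 = 0.41. Power is 63% pooled against about 81% adjusted.
- A 1 SD difference on one variable only: 0.5/√1.25 = 0.45. Power is 72% pooled against 81% adjusted.
- No group difference: 82.5% pooled against 81.2% adjusted. This is the price of one degree of freedom.

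**Does the equal quota cause it?** At d = 1 and r_w = 0, a 9/21 split still gives 15.4% positive pooled tests, against 18.9% at 15/15. At an assumed 20:80 mix the pooled r is 0.16/1.16 = 0.14, against 0.20. Most of the effect is present in any cohort that mixes resections; the quota adds a little.

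**Case mix and the primary outcome.** The shift of the overall mean is (0.5 − p) × group difference, where p is the natural sublobar share. The standard error is 1/√30 = 0.183 SD. An assumed 40% share and 0.5 SD give 0.05 SD (0.3 SE). An assumed 30% share and 1 SD give 0.20 SD (1.1 SE). No objective asks for a case-mix mean, and the within-patient comparison stays valid.

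**What the text commits to.** Set side by side, section 1 fixes the groups, the objectives fix the questions, and no sentence joins or separates the two. A one-sample analysis is therefore an inference from silence. The objective on mediators can also be read as a comparison of time courses, which is how the outcome measures are laid out; the calculation above would then not apply to it.

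**The case for a change.** The best case for a change is that the purpose of a quota group is part of the study question and not a detail of the test. As worded, an analysis plan could pool or stratify and comply equally, although the two answer different questions. The Detailed description presents lung ultrasound as a way to identify patients at high risk of complications. Resection size is known anyway, so an association that exists only because lobectomy patients differ from the rest would not show that ultrasound adds information. The Protocol also offers a route from analgesia to the oxygenation data: the Air-Test requires a pain score below 4, and the room-air blood gas follows that test. Stratifying costs almost nothing.

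Part of this stands. The role of the groups is unstated, group-specific results would help a reader, and a group difference could not be attributed to resection size alone.

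It does not show that the plan is wrong. The objectives ask whether mLUSS detects change after lung resection, not whether it does so among patients with the same resection. If extent of surgery causes the injury, conditioning on it removes part of the signal sought, so the within-group estimate complements the overall one and does not correct it. Whether group enters as a stratum or covariate is commonly settled in a statistical analysis plan, which is not at hand. The remaining suggestions (calling enrolment consecutive within group, noting the equal mix, adding a caveat on analgesia) reword what section 1 and the Anaesthesia protocol already disclose and alter no result.

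**Conclusion.** No change to the plan is needed. The gap is real but small: two groups are recruited and no objective gives them a role. Analysts can fill it sensibly, since group is known for every patient and overall and by-group relations can be shown together at a cost of about one percentage point of power (82.5% to 81.2% for a correlation of 0.5 when the groups do not differ).

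The possible distortion runs from negligible (6% against 5% at 0.5 SD with aligned differences) to large (54% at 1.5 SD). It arises only if the analysis ignores group, if changes are correlated across patients, and if the groups differ substantially. The Protocol states none of these conditions and gives no group difference from which to judge the last. The severe masking case also needs opposing group effects, for which the Protocol offers no reason. Only two secondary objectives of a 30-patient observational study are touched; the primary before-and-after comparison is not.
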